2.3.5 Diagnosis and extent of cancer

Diagnosis and extent of cancer will be listed, including all of the information collected in eCRF.

2.4 Protocol deviations

All protocol deviations will be finalized before database lock. For the purpose of excluding patients from the analysis sets defined in [Section 2.2](#), the protocol deviations and non-protocol deviations and severity codes are defined in [Table 2-1](#).

Table 2-1 Protocol deviations and non-protocol deviations

Analysis set	Protocol deviations with ID [severity codes leading to exclusion]
Full analysis set	[GCP01] The patient was enrolled and the ICF was not signed [511]
Safety set	[PROC01] Patient has had at least one dose of INC280, but has no post-baseline safety assessment [2]
Dose-determining set	[PROC04] For patients in dose-determining part: Patient did not have sufficient safety assessments by Cycle 2 Day 8 for the investigator to complete the Dose Decision Analysis [16] [PROC09] For patients in dose determining part: Patient did not receive INC280 at the planned dose, BID for at least 21 days within the first four weeks of treatment and did not experience a qualifying AE during the first four weeks [16]
Pharmacokinetic analysis set	[PROC02] Patient has no PK sample collected for INC280 [24]
Other	[COMD01] Patients participate in additional parallel investigational drug or device studies [256] [COMD02] Patient received another anticancer therapy other than the study treatments while on the study [256]

[511] exclude from all analysis [2] exclude from safety analysis [16] exclude from dose-determining set [24] exclude from dose-determining set and pharmacokinetic analysis set [256] exclude from date only

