10.5.3.2 Adverse events (AEs)

All AEs recorded during the study will be summarized. The incidence of treatment-emergent AEs (new or worsening from baseline) will be summarized by primary system organ class, severity based on the National Cancer Institute's Common Terminology Criteria for Adverse Events (CTCAE) current edition version 4.03, type of AE, and relationship to the study drug by study Part. Deaths reportable as SAEs and non-fatal SAEs will be listed by patient and tabulated by primary system organ class, type of AE, and study Part.

Qualifying AEs will be separately listed by primary system organ class, worst grade based on the CTCAE current edition version 4 and type of AE. The DDS will be used.

Any other information collected (e.g. start/end dates and duration of AE, severity or relatedness to study medication) will be listed as appropriate. For patients undergoing intra-patient escalation to doses other than their initially received dose level, data up to the first intra-patient escalation will be summarized and all post-escalation data will only be listed.

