2.2 Analysis sets

Full Analysis Set

The Full Analysis Set (FAS) comprises all patients who received at least one dose of INC280. The FAS will be used for all listings of raw data. Unless otherwise specified the FAS will be the default analysis set used for all analyses.

Safety Set

The Safety Set includes all patients from the FAS who have received at least one dose of INC280 and had at least one valid post-baseline safety assessment.

Please note: A “**no**” to indicate that the patient had no AEs (on the AE eCRF) constitutes a valid safety assessment.

Per-protocol Set

Not applicable. As the study did not meet the planned enrollment, supportive analysis with PPS is no longer of clinical interest.

Dose-determining analysis set

The dose-determining set (DDS) consists of all patients from the safety set (who are in the Dose-Determining Part) who either meet the minimum exposure criterion and have sufficient safety evaluations (as determined by the Investigators and Novartis), or who have experienced a qualifying AE during the first four weeks of treatment.

A patient is considered to have met the minimum exposure criterion at a dose level if they receive INC280 at the planned dose, BID for at least 21 days within the first four weeks of treatment ($\geq 75\%$ planned administration). Patients who do not experience a qualifying AE during the first four weeks are considered to have sufficient safety evaluations if they have been observed for ≥ 28 days following the first dose, and are considered by both the Sponsor and Investigators to have enough safety data to conclude that a qualifying AE did not occur.

Pharmacokinetic analysis set

The pharmacokinetic analysis set (PAS) consists of all patients who provide an evaluable PK profile. A profile is considered evaluable if all of the following conditions are satisfied:

- Subject receives one of the planned treatments
- Subjects provides at least one primary PK parameter
- Subject did not vomit within 4 hours after the dosing of INC280

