2.9 Safety analysis

Summaries and listings described in this section will be done by study treatment groups based on the Safety set.

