2.9.1.3 AE summaries

AE summaries will include all AEs occurring during on-treatment period (Section 2.1.1). All AEs collected in the AE (e)CRF page will be listed along with the information collected on those AEs e.g. AE relationship to study drug, AE outcome etc. AEs starting during the post-treatment period will be flagged in the listings.

AEs will be summarized by number and percentage of patients having at least one AE, having at least one AE in each primary system organ class (SOC) and for each preferred term (PT) using MedDRA coding. A patient with multiple occurrences of an AE will be counted only

once in the respective AE category. A patient with multiple CTCAE grades for the same preferred term will be summarized under the maximum CTCAE grade recorded for the event. AE with missing CTCAE grade will be included in the 'All grades' column of the summary tables.

In AE summaries the SOC will be presented alphabetically and the PTs will be sorted within primary SOC in descending frequency, based on their frequency in the 'All Patients' column.

The following AE summaries will be produced by study treatment group:

- Overview of AE
- AEs regardless of study treatment relationship by SOC, PT and maximum grade
- AEs regardless of study treatment relationship by PT and maximum grade
- AEs suspected to be study treatment related by PT and maximum grade
- SAEs regardless of relationship to study treatment by PT and maximum grade
- SAEs suspected to be study treatment related by PT and maximum grade
- Summary of qualifying AE for dose decision analysis (Dose determining part only)
- AEs leading to discontinuation of study treatment regardless of relationship to study treatment by PT and maximum grade
- AEs leading to discontinuation of study treatment suspected to be study treatment related by PT and maximum grade
- AEs requiring dose adjustment/interruption by SOC, PT and maximum grade
- AEs requiring additional therapy by SOC, PT and maximum grade

Additionally, for the legal requirements of ClinicalTrials.gov and EudraCT, two required tables on on-treatment adverse events which are not serious adverse events with an incidence greater than 5% and on on-treatment serious adverse events and SAE suspected to be related to study treatment will be provided by system organ class and preferred term on the safety set population.

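### SAP Table 2-1 and SAP 2.9 depart from the protocol's dose-determining set rules: a missing PK sample removes a patient from that set, and the qualifying-AE summary falls on the Safety Set

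*SAP*

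**What the plan says.** **DDS membership.** Protocol 10.1.4 and SAP 2.2 give a Dose-Determining patient two routes into the DDS: minimum exposure plus sufficient safety evaluations, "or who have experienced a qualifying AE during the first four weeks of treatment". The second route stands alone. Neither document asks for a PK sample.

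**Exclusion codes.** SAP 2.4, Table 2-1, lists the deviations that take patients out of the sets defined in SAP 2.2. Three can remove a patient from the DDS:

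- PROC09 (planned dose not received for at least 21 days) has an explicit exception. It applies only when the shortfall occurred "within the first four weeks of treatment and did not experience a qualifying AE during the first four weeks [16"].
- PROC04 has no such exception: "Patient did not have sufficient safety assessments by Cycle 2 Day 8 for the investigator to complete the Dose Decision Analysis [16"].
- PROC02 sits in the PK row: ["PROC02] Patient has no PK sample collected for INC280 [24"]. The table footnote explains the code: ["24] exclude from dose-determining set and pharmacokinetic analysis set".

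**Reporting of qualifying AEs.** Protocol 10.5.3.1 makes the Safety Set the default for safety analyses. Protocol 10.5.3.2 then overrides that default for qualifying AEs, which are displayed by "worst grade based on the CTCAE current edition version 4 and type of AE. The DDS will be used". SAP 2.9 opens with one rule for the whole section: "Summaries and listings described in this section will be done by study treatment groups based on the Safety set". The list in SAP 2.9.1.3 includes "Summary of qualifying AE for dose decision analysis (Dose determining part only") and names no other set. SAP 2.6 keeps the Bayesian model and its posterior summaries on the DDS. SAP section 4 declares only the dropped per-protocol analyses.

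**The concern.** The DDS is the denominator for first-28-day tolerability at 300 mg bid in HCC patients. Its definition protects one kind of patient in particular: someone who has a qualifying AE and then stops early, with short exposure or incomplete follow-up. A coding table that removes such a patient for an unrelated reason takes an event out of the numerator and the denominator together, and so biases the rate down.

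The Safety Set has the opposite fault. It can hold patients who were not observed long enough to show that no qualifying AE occurred. Counting them as event-free dilutes the rate. Under the present wording the CSR would carry a posterior on one population and a summary of the same events on another, with nothing in the SAP to explain a difference.

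**Working it through.** **Step 1. Compare each code with the DDS definition.**

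| Code | Ground for exclusion | Ground in the DDS definition? | Qualifying-AE exception? |
|---|---|---|---|
| PROC09 | Exposure | Yes | Yes, written out |
| PROC04 | Safety assessments by Cycle 2 Day 8 (21 + 8 = day 29) | Yes | Not written; can be inferred |
| PROC02 | No PK sample | No | No |

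PROC02 contradicts the definition outright. PROC04 does not have to: SAP 2.2 defines sufficient evaluations only for patients without a qualifying AE, and PROC04 asks whether the dose decision analysis could be completed, which a qualifying AE already allows.

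**Step 2. How likely is PROC02?** Protocol Table 7-5 schedules 18 samples per Dose-Determining patient: seven on Cycle 1 Day 1 (one of them before the first dose), one on Day 2, and ten later. PROC02 needs none to have been collected from a treated patient. Even a patient who stopped in week 2 would have had 7 + 1 = 8 scheduled samples.

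**Step 3. Effect of the Safety Set denominator.** Protocol 1.2.1.2.2 reports 8 patients in the Dose-Determining Part. Protocol 4.1 requires at least 6 evaluable. I assume that all 8 are in the Safety Set and that the minimum of 6 held, so at most 8 − 6 = 2 patients are outside the DDS. By definition every Safety Set patient in this part with a qualifying AE is also in the DDS, so if the codes are applied correctly only the denominator differs. The number of events is not given; I take 0, 1 or 2.

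| Events | Safety Set (8) | DDS of 6 | DDS of 7 | DDS of 8 |
|---|---|---|---|---|
| 0 | 0% | 0% | 0% | 0% |
| 1 | 1/8 = 12.5% | 1/6 = 16.7% | 1/7 = 14.3% | 12.5% |
| 2 | 2/8 = 25.0% | 2/6 = 33.3% | 2/7 = 28.6% | 25.0% |

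The reported rate is at worst 6/8 = 0.75 of the DDS rate.

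**Step 4. Effect on the DDS posterior if a code removed a patient with an event.** I rebuilt the model of protocol Appendix 5: logit π(d) = log α + β log(d/400), with (log α, log β) bivariate normal as in Table 14-16 (means −1.940 and 0.092, SDs 1.040 and 0.926, correlation 0.043), by grid integration. As a check, it returns all seven rows of Table 14-18 for 0 to 6 events in 6 patients: 600, 500, 300, 200, 100, none, none. Posterior mean rate at 300 mg bid:

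- true 1/7 analysed as 0/6: 0.122 becomes 0.070
- true 1/8 analysed as 0/7: 0.115 becomes 0.066
- true 2/8 analysed as 0/6: 0.178 becomes 0.070

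These use the printed prior, which Appendix 5 allows to be updated. They show what one miscoded patient would do, not that there is one.

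**The case against.** The other side has four fair arguments.

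*PROC04 is not a conflict.* Its day-29 cut-off mirrors the 28-day observation rule in SAP 2.2, and PROC09 needs its exception written out because it is a mechanical dose count. This stands. A reader might infer that PROC04 removes patients with a qualifying AE; the text permits that reading but does not require it.

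*PROC02 will almost never apply.* This also stands, and it limits the effect. It does not make the code right.

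*The analysis-set shift may be nominal.* Protocol 10.5.3.2 speaks of listing qualifying AEs, and a listing is the same on either set. The output shells are a separate document and may name the DDS. This narrows the point to the denominator of a summary. But SAP 2.9.1.3 specifies a summary, and as written the section-level rule puts it on the Safety Set.

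*No remaining decision depends on it.* This stands. A reader might infer that a miscoded patient could have let 600 mg bid pass the overdose limit. The documents do not support that as a live risk. The Amendment 2 study update says that the Dose-Determining Part was complete and expansion at 600 mg bid had begun in December 2013. Protocol 6.2.4 sets the tablet dose from other studies. SAP section 1 says that enrolment was permanently halted after 25 December 2016. Protocol 6.2.2 also requires external safety data in the model, so results on the printed prior alone do not reconstruct the decision.

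**Conclusion.** Two mismatches hold on the text. PROC02 removes a patient from the DDS on a ground that its definition does not contain. The qualifying-AE summary moves from the DDS to the Safety Set without being declared. The missing exception in PROC04 is a matter of consistent wording.

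The size is small and conditional. If the DDS has 6 of the 8 enrolled patients, one event reads 12.5% instead of 16.7% and two read 25.0% instead of 33.3%; if it has all 8, there is no difference. The posterior mean at 300 mg would roughly halve if one patient with an event were coded out, but the documents name no such patient and PROC02 is unlikely to apply. The figures assume a Safety Set of 8, at least 6 evaluable patients, and 0 to 2 events. The effect stays within the CSR's descriptive qualifying-AE rate and DDS posterior. It reaches neither the dose decision already taken nor the TTP result. This is worth correcting but is not a serious defect.

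**What to change.** 1. Recode PROC02 in SAP Table 2-1 so that it excludes from the PK analysis set only.
2. State in SAP 2.9.1.3 that the qualifying-AE summary uses the DDS. If the Safety Set is intended, list the change in SAP section 4 with a reason.
3. Add the qualifying-AE exception from PROC09 to PROC04, for consistency.
4. Before database lock, check the 8 Dose-Determining patients for PROC02 or PROC04 together with a qualifying AE. If there is none, items 1 and 3 change no output.

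The cost is one code, one sentence, one clause and a check of 8 records, in a SAP amendment before lock. No new data or analyses are needed.

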2.5 Study treatment

Summaries and listings described in this section will be done by study treatment groups based on the Safety set.

2.5.1 Data handling

2.5.1.1 Data Imputation

The following rule should be used for the imputation of date of last administration (please refer to [Sections 2.1.1](#)) for a given study treatment:

If the date of last administration is completely or partially missing and the EOT eCRF page is available (prior to any death date or withdrawal of consent date, if available):

Case 1: The date of last administration is completely missing, and the EOT visit date is complete, then this latter date should be used.

Case 2: Only Year(yyyy) of the dose end date is available and yyyy < the year of EOT date:

Use Dec31yyyy

Case 3: Only Year(yyyy) of the dose end date is available and yyyy = the year of EOT date:

Use EOT date

Case 4: Both Year(yyyy) and Month (mm) are available for the date of last administration, and yyyy = the year of EOT date and mm < the month of EOT visit:

Use last day of the Month (mm).

All other cases should be considered as a data issue and the statistician should contact the data manager of the study.

After imputation, compare the imputed date with the start date of that specific record, if the imputed date is < start date of that record

Use the start date of that record.

Patients with missing start dates are to be considered missing for study treatment related calculations described in [Section 2.5.2](#) and no imputation will be made. If the date of first administration is missing, then the date of last administration should not be imputed.

2.5.2 Data analysis

Duration of exposure, actual cumulative dose, dose intensity (DI) and relative dose intensity (RDI) will be summarized for the study treatment. Duration of exposure will be categorized into time intervals; frequency counts and percentages will be presented for the number(%) of patients in each interval. The number (%) of patients who have dose reductions or interruptions, and the reasons, will be summarized by study treatment.

Patient level listings of all doses administered on treatment along with dose change reasons will be produced.

The safety set will be used for all summaries and listings of study treatment.

2.5.2.1 Duration of exposure to study treatment

Duration of exposure to study treatment (days) = (last date of exposure to study treatment) – (date of first administration of study treatment) + 1.

The last date of exposure to study treatment is the last dates of exposure to INC280, i.e., a patient had a permanent discontinuation of the study drug on 06-Jan-2013 after being put on a temporary interruption since 01-Jan-2013. In this case the last date of exposure is 31-Dec-2012.

Summary of duration of exposure of study treatment will include categorical summaries (based on time intervals: <=3 weeks, 3-<=9 weeks, 9-<=18 weeks and >18 weeks) and continuous summaries (i.e. mean, standard deviation etc.) using units of days.

2.5.2.2 Cumulative dose

Cumulative dose of a study drug is defined as the total dose given during the study drug exposure and will be summarized.

The **planned cumulative dose** for the study drug refers to the total planned dose as per the protocol up to the last date of study drug administration. The planned cumulative dose is not summarized/listed. It is used for relative dose intensity calculations.

The planned cumulative dose is the planned total daily dose * Duration of exposure to study drug (days).

The **actual cumulative dose** refers to the total actual dose administered, over the duration for which the patient is on the study treatment as documented in the Dose Administration eCRF, i.e., the actual cumulative dose is the sum of the non-zero doses recorded over the dosing period and the planned cumulative dose is the planned starting dose summed over the same dosing period.

For patients who did not take any drug, the actual cumulative dose is by definition equal to zero for that drug.

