During the Dose-Determining Part, at least six patients will be enrolled and treated with INC280 at 300 mg bid (capsule). Safety, full PK profiles of INC280 on Cycle 1, Days 1, 2, 15 and 16, predose PK samples on Cycle 2 Day 1 and Cycle 3 Day 1, demographics and other baseline characteristics will be collected in these patients ([Section 7.1.2.3](#), [Section 7.2.2](#) and [Section 7.2.3](#)).

A dose decision analysis based on safety and PK data will be conducted when patients from Dose-Determining cohort have completed 28 days treatment and data from at least 6 patients are evaluable for the dose-determining set (DDS) (see [Section 10.1](#)). The analysis will be guided by the medical review of available clinical, laboratory, and PK data, as well as the recommendation from the Bayesian Logistic Regression Model (BLRM) (see [Section 6.2.2](#) for details on the decision process).

Novartis and the principal investigators will have a dose decision meeting to discuss and evaluate the data. At this meeting, Novartis and the principal investigators must reach consensus on the dose level to be used in the Dose Expansion Part. Novartis will prepare minutes from this meeting and circulate them to each investigator for comments prior to finalization. The Expansion Part dose will be communicated to all investigators in writing.

Patients in the Dose-Determining Part who have not experienced a dose reduction will be allowed to switch to the confirmed Expansion Part dose, if different from the Determining Part dose, under consultation from the Investigator with Novartis.

Dose Expansion Part

Once the Expansion Part dose has been confirmed, approximately 50 patients in total will be enrolled, among which around 25 to 40 patients will have the c-MET positive status as specified in the inclusion criteria ([Section 5.2](#)).

Detailed information on all patients will be collected and reported (see [Section 10](#) for details).

Follow-up

All patients will be followed-up as described in [Section 7.1.5](#). At minimum, patients must complete the safety follow-up assessments 30 days after the last dose of the study treatment.

All patients will be followed until progressive disease (PD), death or withdrawal of consent regardless of any drug discontinuation. All patients will be followed for OS for a duration of at least 6 months after last patient first dose.

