6.2.4 Dose determining for tablet formulation

A relative bioavailability study in HVs, CINC280X2103 study, was conducted to compare the relative bioavailability of INC280 tablet to INC280 capsule. The results of this study showed that following a single oral administration of 600 mg INC280 in healthy subjects, both formulations had similar Tmax; tablets however provided higher systemic exposures (Cmax and AUC) and lower inter-subject variability. The exposure geometric mean ratios (tablet vs. capsule) were around 2 to 3. As of 3-Nov-2014, preliminary tablet PK data are available from 16 patients of tablet cohorts at different doses in various INC280 studies (i.e., 200 and 400 mg bid single agent in CINC280X1101 study, 200 mg bid in combination with gefitinib in CINC280X2202 study, and 400 mg bid single agent in CINC280X2102 study). INC280 tablet showed generally lower inter-subject variability than capsule (CV% typically $<50\%$ for tablet, whereas $>50\%$ for capsule). Based on the limited data, mean AUC and Cmax at steady-state following administration of INC280 tablets at 400 mg bid was higher than that following capsules at 600 mg bid (RP2D in CINC280X2102 study), but in the range considering the CV%. Based on the tablet PK and safety data from these studies, the dosage of INC280 at 400 mg bid in tablet has been declared as RP2D in CINC280X2102 study, and is further evaluated in CINC280X1101 study and CINC280X2202 study. Therefore, 400 mg bid is determined to be the dose of tablet formulation in the dose expansion part of this study. When the INC280 tablet formulation is available, patients who are newly enrolled may start at INC280 400 mg bid tablet treatment. Patients who have been treated with INC280 600 mg bid capsules, in compliance with the local regulation, may switch at the beginning of the next scheduled visit with INC280 400 mg bid tablet treatment.

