- A patient with disease progression may be allowed to continue study treatment if it is in the best interest of the patient to continue treatment. Examples of situations that may allow for continuation of therapy include cystic lesions, mixed responses, and new brain metastases that are treatable with stereotactic radiotherapy or surgery.

Table 6-3 and **Table 6-4** describe respectively for the Dose-Determining Part and Dose Expansion Part, the starting dose and the study drug dose modification to be followed in case of study drug related toxicities. For each patient in Dose Expansion Part treated with INC280 tablets, a maximum of 2 dose level modifications is allowed after which the patient must be discontinued from treatment. The lowest dose allowed, 200 mg BID in tablets is expected to be pharmacologically active, as the observed steady state plasma trough concentrations ([CINC280X1101], [CINC280X2202], n=6) were above the concentration associated with full cMET inhibition in xenograft mice models (EC90, 120 nM total concentration).

Table 6-3 Dose-Determining Part study drug dose reductions

Dose level	Dose and schedule (capsule)	Increment from previous dose
-1	200 mg bid	-33% of starting dose
0	300 mg bid	Starting dose for Dose-Determining Part

Table 6-4 Dose Expansion Part study drug dose reductions

Dose level	Dose and schedule (capsule)	Increment from previous dose
-1	450 mg bid (capsule)	-25% of starting dose
0	600 mg bid (capsule)	Starting dose for Expansion Part

Dose level	Dose and schedule (tablet)	Increment from previous dose
-2	200mg bid (tablet)	-50% of starting dose
-1	300 mg bid (tablet)	-25% of starting dose
0	400 mg bid (tablet)	Starting dose for Expansion Part

Table 6-5 Recommended dosing guidelines for study drug-related toxicities

Recommended dose modifications of INC280	
Worst toxicity CTCAE v4.03 grade	Recommended dose modifications any time during a cycle of therapy, including intended day of dosing
Hematologic	
ANC decreased (Neutropenia) Grade 1 (LLN - 1500/mm ³ or LLN – 1.5x10 ⁹ /L) Grade 2 (< 1500 - 1000/mm ³ or <1.5 – 1.0x10 ⁹ /L) Grade 3 (< 1000 - 500/mm ³ or < 1.0 – 0.5x10 ⁹ /L) Grade 4 (< 500/mm ³ or < 0.5x10 ⁹ /L)	Maintain dose level Maintain dose level Discontinue dose until resolved to ≤ grade 1 or baseline, then: If resolved in ≤ 7 days, then maintain dose level If resolved in > 7 days, then ↓ 1 dose level Discontinue dose and patient from study treatment.

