10.3 Treatments (study treatment, concomitant therapies, compliance)

10.3.1 Study treatment

The actual dose and duration in days of INC280, as well as the dose intensity (computed as the ratio of actual dose received and actual duration) and the relative dose intensity (computed as the ratio of dose intensity and planned dose received/planned duration) will be listed and summarized by means of descriptive statistics in the clinical study report (CSR). Categories for relative dose intensity of INC280 will be specified as < 0.5 , $\geq 0.5 - < 0.75$, $\geq 0.75 - < 0.9$, ≥ 0.9

- < 1.1 and \geq 1.1. The number and proportion of patients within each category will be presented by treatment, for cycle 1 alone and for overall treatment duration. The FAS will be used.

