2.5.2.3 Dose intensity and relative dose intensity

Dose intensity (DI) for patients with non-zero duration of exposure is defined as follows:

$DI \text{ (dosing unit / unit of time)} = \text{Actual Cumulative dose (dosing unit)} / \text{Duration of exposure (unit of time)}$.

For example, for INC280, the dosing unit is mg and actual cumulative dose is 1200 mg, and the unit of time is a day and duration of exposure is 18 days, then

$$\begin{aligned} DI \text{ (mg/day)} &= \text{Actual Cumulative dose (mg)} / \text{Duration of exposure (day)} \\ &= 1200 \text{ (mg)} / 18 \text{ (day)} = 66.7 \text{ (mg/day)} \end{aligned}$$

For patients who did not take any drug the DI is by definition equal to zero.

Planned dose intensity (PDI) is defined as follows:

$PDI \text{ (mg / day)} = \text{Planned Cumulative dose (mg)} / \text{Duration of exposure (day)}$.

Relative dose intensity (RDI) is defined as follows:

RDI = DI (mg / day) / PDI (mg / day).

DI and RDI will be summarized for the study drug. The RDI will be tabulated using the following intervals: <0.5, >=0.5-<0.75,>=0.75-<0.9, >=0.9-<1.1, >=1.1.

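### The SAP's relative dose intensity keeps the capsule starting dose as the plan after the permitted switch to tablets, so a fully compliant switcher is shown as under-dosed

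*SAP*

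**What the plan says.** Protocol 10.3.1 defines RDI as "computed as the ratio of dose intensity and planned dose received/planned duration". It does not say that planned dose means starting dose, and it does not mention switches.

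SAP 2.5.2.2 is more specific. It opens by calling planned cumulative dose the total planned under the protocol. It then gives a formula with a single planned daily dose multiplied by duration of exposure, and ends by saying that "the planned cumulative dose is the planned starting dose summed over the same dosing period". The numerator is the sum of all recorded doses in mg, whatever the formulation. SAP 2.5.2.3 divides one by the other: "The RDI will be tabulated using the following intervals", with cut points at 0.5, 0.75, 0.9 and 1.1.

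The protocol permits two changes of dose that are not toxicity reductions:

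- **Capsule to tablet (Protocol 6.2.4).** Expansion patients on 600 mg bid capsules "may switch at the beginning of the next scheduled visit with INC280 400 mg bid tablet treatment". Table 6-4 puts 600 mg bid capsule and 400 mg bid tablet at level 0, each labelled "Starting dose for Expansion Part".
- **Dose-Determining to Expansion dose (Protocol 4.1).** Patients "who have not experienced a dose reduction will be allowed to switch to the confirmed Expansion Part dose". Protocol 1.2.1.2.2 gives the two doses as 300 mg bid and 600 mg bid.

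SAP 2.1 says that formulation will be considered where appropriate, and that Dose-Determining data are reported at the initial dose level even after escalation. Neither statement gives a rule for the RDI denominator.

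**The concern.** Milligrams of capsule and tablet are not interchangeable in this trial. Protocol 6.2.4 reports, from the healthy-volunteer comparison at 600 mg: "The exposure geometric mean ratios (tablet vs. capsule) were around 2 to 3". It adds that, on limited patient data and within the observed variability, mean steady-state exposure on "INC280 tablets at 400 mg bid was higher than that following capsules at 600 mg bid". Scoring a tablet patient in mg against the capsule dose therefore shows a shortfall that the protocol does not treat as one.

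Dose intensity is a named tolerability endpoint (SAP Table 1-1), and the tolerability text in SAP 2.9.4 relies on RDI. A reader of the banded table would take a value below 0.9 as missed or reduced dosing, when the patient may have taken every prescribed dose. Actual cumulative dose and dose intensity have the same weakness, because both add mg across formulations.

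Two neighbouring rules are also unsettled. SAP 2.5.2.4 derives reductions from the direction of change in prescribed dose level, a term it does not define, so it is unclear whether a 600 to 400 mg conversion counts. SAP 2.9.1.3 summarises all on-treatment adverse events, whereas Protocol 10.5.3.2 says that data after intra-patient escalation are only listed.

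**Working it through.** **The SAP's own figure.** SAP 2.5.2.3 works one dose-intensity example: 1200 mg / 18 days = 66.7 mg/day. This reproduces. The documents give no RDI for a switcher.

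**Inputs (mg/day, twice the bid dose).** From Protocol Tables 6-3 and 6-4: capsule level 0 = 1200, level -1 = 900; tablet level 0 = 800, level -1 = 600; Dose-Determining start = 600. Let f be the share of exposure before the switch. The documents give no switch times, so f is an assumption and is varied from 0 to 1.

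**Tablet switch, all doses taken, SAP rule.**

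RDI = [f x 1200 + (1 - f) x 800] / 1200 = f + (1 - f) x 2/3

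- f = 0.5: (600 + 400) / 1200 = 0.83, in the 0.75 to <0.9 band.
- RDI = 0.9 at f = 0.70, so a switch in the last 30% of exposure stays in the 0.9 to <1.1 band.
- RDI = 0.75 at f = 0.25; below that the patient falls into the 0.5 to <0.75 band.
- Illustration with an assumed switch after 63 capsule days: on tablet day 28, (63 x 1200 + 28 x 800) / (91 x 1200) = 0.897.

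**Comparator.** One level down for half of exposure, no switch: capsule (0.5 x 1200 + 0.5 x 900) / 1200 = 0.875; tablet (0.5 x 800 + 0.5 x 600) / 800 = 0.875. A compliant switcher lies a band below this patient only when f < 0.25.

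**Candidate remedies, mid-exposure switch.**

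| Patient | SAP rule | Planned mg updated at switch, mg pooled | Duration-weighted mean of period ratios |
|---|---|---|---|
| Compliant switcher | 1000/1200 = 0.83 | 1000/1000 = 1.00 | 0.5 x 1 + 0.5 x 1 = 1.00 |
| Switch, then tablet level -1 to the end | 900/1200 = 0.75 | 900/1000 = 0.90 | 0.5 x 1 + 0.5 x 600/800 = 0.875 |
| No switch, one level down for half | 0.875 | 0.875 | 0.875 |

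Pooling mg with an updated denominator puts the same toxicity reduction in two different bands (0.90 and 0.875). The duration-weighted mean does not.

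**300 to 600 mg bid, SAP rule.** RDI = [f x 600 + (1 - f) x 1200] / 600 = 2 - f, which is 1.5 at f = 0.5 and at least 1.1 whenever f <= 0.90. If the patient escalates at mid-exposure and then misses half of the later doses, RDI = (0.5 x 600 + 0.5 x 600) / 600 = 1.00. Against the dose planned in each half it is 600 / (300 + 600) = 0.67.

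**The case against.** Starting dose is a sound reference for toxicity reductions, because it keeps a reduced patient below 1. The switch is optional and no document reports that anyone made it. Dose listings with reasons, and summaries of interruptions and reductions, let a reader see what happened. SAP 2.1 promises to consider formulation, the opening words of SAP 2.5.2.2 could be read as following a permitted switch, and the programming specifications, which are not available here, may hold a rule. These arguments keep the point small but do not remove it: the explicit closing clause of SAP 2.5.2.2 names the starting dose, and a listing does not correct a banded table.

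A reader might infer more than the documents support:

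- **That compliant switchers generally rank below patients with toxicity reductions in the table.** At mid-exposure, 0.83 and 0.875 share a band. Against that comparator the band differs only for f < 0.25.
- **That 1.5 after escalation is an error.** Protocol Section 10 and SAP 2.1 both report Dose-Determining data at the initial dose level, and RDI against the initial dose fits that rule. The value is legitimate, but it measures escalation rather than compliance and can mask missed doses.
- **That the protocol contradicts itself on adverse events after escalation.** Listing later events under the initial dose group satisfies both Protocol Section 10 and 10.5.3.2. The mismatch is between SAP 2.9.1.3 and Protocol 10.5.3.2.
- **That the tablet conversion will be counted as a reduction.** SAP 2.5.2.4 leaves this open either way.

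**Conclusion.** The point holds for the capsule-to-tablet switch, as a minor one. Under the written rule a fully compliant switcher scores between 0.67 (a limit as f nears 0, not reached) and 1.00. The score is 0.83 at mid-exposure and leaves the on-plan band when less than 70% of exposure precedes the switch. These figures assume every dose is taken and no other dose change.

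For Dose-Determining patients who move to the Expansion dose, the issue is labelling and interpretation, not a wrong denominator.

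The effect on the summary table cannot be sized. The only counts are enrolment at 28 September 2015 (28 Expansion, 8 Dose-Determining; Protocol 1.2.1.2.2), and the number of switchers is not given and may be zero. The outputs are descriptive, and neither the time-to-progression analysis nor the Bayesian logistic regression model uses RDI.

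**What to change.** Analysis rules only; doses and reporting groups stay as they are.

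1. **SAP 2.5.2.2 and 2.5.2.3.** For each formulation period, divide actual dose by the level-0 planned dose for the formulation being taken. Combine periods as a mean of these ratios weighted by days of exposure, not by adding mg across formulations. Do not reset the planned dose at a Table 6-3 or 6-4 toxicity reduction.
2. **Cumulative dose and dose intensity in mg.** Report these separately by formulation for switchers.
3. **SAP 2.5.2.4.** State that a capsule-to-tablet conversion between equal Table 6-4 levels is not counted as a dose reduction.
4. **Escalated Dose-Determining patients.** Footnote that RDI is relative to the initial dose, or report it up to the switch and after it.
5. **Adverse events (separate point).** Align SAP 2.9.1.3 with Protocol 10.5.3.2, or record the departure in SAP Section 4. If summaries stop at first escalation, escalated patients contribute slightly less time.

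The cost is SAP wording and programming, on one condition. Protocol 6.5 has prescribed doses and dose changes recorded on the dosage administration record, but nowhere says that formulation is captured at each change. The SAP should therefore name the data source that identifies formulation.
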